## **D. Design and Methods**

### **(1) Study Design**

Prospective, non-blinded, Interventional study

We plan to recruit up to 60 concussed patients, equally randomized to an intervention group who participate in the at home exercise program, or those who undergo the same testing but receive the standard of care given by their physician. Subjects will be recruited from Boston Children's Hospital Sports Medicine Clinic, The Micheli Center for Sports Injury Prevention as well as affiliated schools, clinics and sports organizations. The subjects and parents/guardians who voluntarily agree to participate will be scheduled for three visits. Upon the first visit, a research coordinator will explain the study and have the subject and parent/guardian sign the "Research Consent Form", approved by the Institutional Review Board of Boston Children's Hospital before participating in the study. Subjects will be required to complete three visits to The Micheli Center for Sports Injury Prevention or Spaulding Hospital in Cambridge for testing.

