The second part of the procedure involves the branching graded exercise test. Subjects will still be monitored using a standard 5-lead ECG and blood pressure measured by oscillometric blood pressure cuff. Throughout the graded exercise test cerebral blood flow will be monitored via TCD or NIRS. The subjects will also be connected to the metabolic cart to measure VO2. The exercise test will continue until the subject reports an increase in symptoms, using the abbreviated concussion symptom inventory or to 85% of their age-predicted maximum heart rate determined by the 5-lead ECG. The subject will be taken off the bike and cool down. Measurements will be taken for an additional five minutes. Both the usual care and intervention group will complete this part of the study.

After completion of testing, the subject will have the ECG, blood pressure cuff, metabolic cart, TCD and NIRS system removed. They will be monitored by a trained professional until symptoms ease or subject's heart rate and blood pressure has returned to resting values.

The final part of the procedure includes the single/ dual-task gait evaluation and VOMS.

Weeks 1-4 (at-home exercise):

Subjects in the intervention group will be advised to participate in aerobic exercise five days a week. This includes walking, biking, jogging and running. While participating in these activities, they will be wearing their Polar Wrist Unit and Heart Rate Monitor to help subjects track their exercise intensity. They will exercise for 20 minutes five times a week at 80% of their heart rate reverse, determined by their resting heart rate and maximum heart rate reached during exercise testing.

Usual care subjects will follow their physician's instructions for exercise and rest. They will also wear the Polar Wrist Unit and Heart Rate Monitor to track their exercise intensity, but will not receive a heart rate specific exercise recommendation.

Study Visit 2 (approximately 4 weeks post-enrollment):

All participants will participate in this visit. Subjects will undergo the same procedures as visit one, including the DHS, HADS, PHQ, PCSI/ PCSS, supine rest, graded exercise test, VOMS and

single/dual- task gait. At this time, the target heart rate for exercise will be adjusted to a new symptom limited heart rate for all participants who are still symptomatic based on the same procedure.

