### **(6) Study Timeline (as applicable)**

Once IRB approval is given we will start the recruitment process. We plan to enroll and complete testing for a total of 60 subjects over the next year.

Timeline for all subjects:

- Recruited from Boston Children's Hospital Sports Medicine clinic
- Comes in within 14 days of injury for study 1 visit
- Comes in 4 weeks later for study 2 visit
- Comes in 4 weeks later for study 3 visit

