## **H. Data Analysis Plan**

This protocol seeks to elucidate the relationship between regional brain blood flow and CO2 during exercise in individuals who have experienced a mild TBI, and to assess the effect of a standardized exercise protocol on cerebral blood flow.

Total hemoglobin concentration in the pre-frontal cortex will be calculated as the sum of oxygenated and deoxygenated hemoglobin (as measured by NIRS) and will serve as a surrogate for regional cerebral blood flow. The brain blood flow and end-tidal CO2 data will be aligned in time. The linear relationship between the two time series will be determined and compared across injury duration and symptom severity. We will use a linear mixed effect model akin to a multiple linear regression model where regional cerebral blood flow is used as the dependent variable, end-tidal CO2 is the independent variable, and symptom duration and amount of exercise are covariates.

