## **I. Statistical Power and Sample Considerations**

To estimate the sample size required to achieve our aims, we used R-language statistical software using a p-value cutoff of 0.05 and minimum statistical power of 0.8. To achieve our specific aim, we will compare the relation between regional blood flow and CO2 responses to a branching exercise protocol, while accounting for injury duration. Given this analysis plan, we estimated that obtaining data from 60 individuals will allow us to detect any relation with an R^2 of 0.31 or higher.

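### Section H compares the flow–CO2 slope across an undefined injury duration with no visit or arm term; if visits are pooled, that comparison is mostly visit number and absorbs exercise and retest effects

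*Combined protocol and SAP*

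**What the plan says.** Section H (Data Analysis Plan) aligns NIRS-derived regional flow with end-tidal CO2 and states: "The linear relationship between the two time series will be determined and compared across injury duration and symptom severity". It then names a linear mixed effect model with flow as outcome and CO2 as predictor, in which "symptom duration and amount of exercise are covariates". Arm, visit, arm-by-visit and injury duration are not listed as terms, and no interaction with CO2 is stated. Section I nonetheless describes the comparison as made "while accounting for injury duration".

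The timing is in section D(6): "Comes in within 14 days of injury for study 1 visit", "Comes in 4 weeks later for study 2 visit" and "Comes in 4 weeks later for study 3 visit". The schedule in D(5) gives Visit 2 as "Study Visit 2 (approximately 4 weeks post-enrollment" and states no window in days. The testing is repeated at each visit in both arms. Section D(1) has up to 60 patients "equally randomized to an intervention group who participate in the at home exercise program" or to usual care. Usual-care participants wear the same heart-rate monitor.

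**The concern.** Time since injury at any visit is the entry delay (0 to 14 days) plus 0, 28 or 56 days. If all visits contribute, a comparison across time since injury is largely a comparison across visits. Only Visit 1 precedes the programme for everyone. By Visits 2 and 3 half the participants have been assigned 4 or 8 weeks of exercise, and everyone has repeated the test.

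Only concussed patients are recruited, so this comparison is the nearest thing in Section H to an analysis of Aim 1, the effect of concussion on cerebrovascular function. A slope change produced by the randomised programme, or by familiarity with the test, could be reported as the natural course of concussion.

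**Working it through.** **The plan's own figure.** The plan gives no number on this point. Its one computed design figure, R² of 0.31 with 60 individuals (Section I), does not reproduce as a standard multiple-regression F test at 0.05 and 80% power: 60 individuals would detect 0.119 with one predictor and 0.191 with five. That figure plays no part below.

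**Inputs.** From D(5) and D(6): entry within 14 days of injury, and visits at 0, 28 and 56 days after entry. From D(1): 1:1 allocation. Assumed, because the documents do not say: all three visits are pooled, the distribution of entry days, and the width of the visit windows.

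**Step 1: share of time since injury that is visit number.**

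Share = Var(visit offsets) / [Var(visit offsets) + Var(entry days) + window variance].

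- Var{0, 28, 56} = (28² + 0 + 28²)/3 = 522.7 days².
- Var of uniform 0–14 = 14²/12 = 16.3; uniform 3–14 = 11²/12 = 10.1; half at day 0 and half at day 14 = 7² = 49.
- A uniform ±7-day window at two of the three visits adds (14²/12) × 2/3 = 10.9.

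| Entry days | Visit windows | Share due to visit |
|---|---|---|
| Uniform 0–14 | exact | 522.7/539.0 = 97.0% |
| Uniform 3–14 | exact | 522.7/532.8 = 98.1% |
| Uniform 0–14 | ±7 days | 522.7/549.9 = 95.0% |
| Day 0 or day 14 only | exact | 522.7/571.7 = 91.4% |
| Day 0 or day 14 only | ±7 days | 522.7/582.6 = 89.7% |

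The SD of time since injury is √539.0 = 23.2 days pooled and √16.3 = 4.0 days at Visit 1. If only Visit 1 is used, or if injury duration means days from injury to enrolment, the share is zero.

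**Step 2: an exercise effect read as injury duration.** Suppose the programme changes the flow–CO2 slope by D/2 at week 4 and D at week 8, and time since injury has no effect. Write A for arm (0 or 1) and V for visit (0, 1, 2). The slope change is (D/2)·A·V.

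- Cov(time, A·V) = 28 × ½ × Var(V) = 28 × ½ × 2/3 = 9.33.
- Apparent change over 56 days = (D/2) × 9.33/539.0 × 56 = 0.485D, which is half the 97% share.
- Across the table above, half the share runs from 0.45D to 0.49D.

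**Step 3: does the planned exercise covariate remove it?** An additive covariate shifts the level of flow, whereas the effect sits in the product with CO2. Simulation with uniform entry and assigned exercise gives about 0.48D with no exercise term, about 0.48D again with exercise entered additively, and about 0 only with an exercise-by-CO2 term. Section H states no such term.

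**Step 4: a retest effect read as injury duration.** If the only true effect is a shift of 1 per visit in both arms, the amount absorbed per 28 days is 28² × (2/3)/539.0 = 0.97. It is still 0.96 with cumulative assigned exercise in the model, because both arms are retested on the same schedule.

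**Step 5: what the design can separate.** Arm is uncorrelated with time since injury. With arm and arm-by-time terms, the usual-care slope on time absorbs none of the exercise effect. With visit in the model, the coefficient on days from injury to Visit 1 absorbs none of the retest shift either.

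**The case against.** The strongest reply is that pooling is nowhere stated. Section H leaves the visits open, and Section I counts 60 individuals, which suits a between-patient comparison. This stands: a reader might infer from the 97% that the plan definitely confuses duration with visit, and the documents do not support that. They do lean towards pooling. The amount of exercise comes most naturally from the home programme, which starts after Visit 1, and a model using it as a covariate presumably includes later visits.

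A reader might also infer that exercise and time cannot be disentangled, or that only Visit 1 is untouched by the intervention. Neither holds. The concurrent usual-care arm is tested at all three visits without the prescribed programme, so arm-by-visit terms recover the exercise effect. Restricting Aim 1 to Visit 1 would discard that eight-week course.

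A third tempting inference is that collinearity between pooled duration and visit makes the estimate unstable, and that splitting the variable cures this. It does not. Pooled duration is entry days plus 28 × visit, so with visit in the model and exact spacing the two versions span the same space and give the same duration coefficient and standard error. Imprecision comes from the 4-day SD of entry delay and remains after the split. The split matters because the plan as written has no visit term.

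Finally, Section H does list an exercise covariate. This deserves credit, but the covariate is achieved exercise, measured after randomisation, and it enters without a CO2 interaction. It does not replace the randomised contrast.

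**Conclusion.** The point holds in conditional form. The firm finding is that injury duration and the contributing visits are undefined, and that no visit or arm term is listed. If the three visits are pooled, about 90–98% of the variation in time since injury is visit number, with 97% under uniform entry over days 0–14. On that same basis, about 0.48D of an exercise effect D on the slope would be attributed to injury duration, and about 97% of a retest effect would be. The exercise leakage can be removed with the design as it stands. Within the usual-care arm, change over visits cannot be divided between time since injury and retesting, and no rewording alters that. This should be corrected before analysis.

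**What to change.** In Section H:

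- Define injury duration as days from injury to Visit 1, and state which visits enter each analysis.
- In the repeated-visit model, include that variable, visit, arm and arm-by-visit, each interacted with end-tidal CO2, with a participant random effect (on the CO2 slope as well as the intercept, since slopes are being compared).
- Read the exercise effect from the arm-by-visit interaction with CO2. Read injury duration only from the between-participant term, with a Visit 1 analysis as support.
- Describe change over visits in usual care as time since injury combined with repeat testing.

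In Section I, give the reference to injury duration the same meaning.

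The cost is wording: no new data or visits. The downside is that the injury-duration estimate rests on a 0–14 day range (SD about 4 days, against 23 pooled) and will be imprecise. The plan should say so in advance, so that a wide interval is not read as absence of a relation.

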## **A. Specific Aims/Objectives**

1. To observe how concussion affects cerebrovascular function and symptoms among adolescents.
2. To investigate the effect of a sub-maximal exercise protocol on cerebrovascular function and concussion symptoms in adolescents who have recently sustained a concussion.

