**Figure 1: Modified sub-maximal exercise protocol**

#### **(4) Definition of Primary and Secondary Outcomes/Endpoints**

- Primary: blood oxygenation level in the prefrontal cortex before and after the administration of the exercise protocol.
- Secondary: the proportion of participants who continue to experience symptoms after the 8-week exercise intervention and the potential confounding variables that contributes to this risk of persistent symptoms.

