#### Study Visit 3 (8 weeks post-enrollment):

All subjects will participate in this visit (usual care and intervention). Subjects will undergo the same procedures as visit one, including completing the DHS, HADS, PHQ, PCSI/PCSS, cerebrovascular function tests, graded exercise test, VOMS and single/ dual-task gait.

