### **F. Data Management Methods**

Medical health information will be saved and input using RedCap survey. There will be an internal RedCap to enter recruitment information and identifying information. It will also include the exercise logs to help blind the PI from knowing which intervention group the subjects are in. The external RedCap will include the surveys, concussion history and test measurements. The information will be stored using the study ID numbers consistent with the rest of the measurements. Data from the heart rate monitors will be securely transferred from the device to a BCH-encrypted computer via USB drive.

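### The plan randomises patients to home exercise or usual care, but specifies no analysis by randomised arm, and its sample size addresses only the flow-CO2 relation

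*Combined protocol and SAP*

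**What the plan says.** - **Aim.** Section A, Aim 2: "To investigate the effect of a sub-maximal exercise protocol on cerebrovascular function and concussion symptoms" in recently concussed adolescents.
- **Design.** Section D(1): up to 60 patients are "equally randomized to an intervention group who participate in the at home exercise program" or to the care their physician would ordinarily give, with the same testing. Section D(5) schedules both arms at enrolment, about week 4 and week 8. Of the last visit it says: "All subjects will participate in this visit (usual care and intervention").
- **Endpoints.** Section D(4) gives as the primary outcome "blood oxygenation level in the prefrontal cortex before and after the administration of the exercise protocol". The other endpoint listed there concerns persistent symptoms and is worded as "the proportion of participants who continue to experience symptoms after the 8-week exercise intervention", together with possible confounders of that risk.
- **Analysis.** Section H names the effect of a standardised exercise protocol on cerebral blood flow as a goal. It then specifies one linear mixed model: regional flow as outcome, end-tidal CO2 as predictor, and "symptom duration and amount of exercise are covariates". The flow-CO2 relation is to be compared across injury duration and symptom severity.
- **Sample size.** Section I uses a 0.05 cut-off and power of at least 0.8. It says that 60 individuals allow detection of a relation with R-squared 0.31 or more, and ties this to flow and CO2 in the branching exercise test.

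**The concern.** Randomisation is useful only if the analysis compares the groups it created. Here assigned arm does not enter the analysis.

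The nearest substitute is amount of exercise, which the plan leaves undefined, and neither reading of it works. If it is home activity, it is behaviour after randomisation. It is monitored in both arms and can depend on how symptomatic the patient is, so its coefficient is an observational association. If it is work done in the graded test, it says nothing about the home programme.

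Two things are at stake. A statement about the programme would rest either on that covariate or on an arm comparison chosen after the data are seen, with three visits and several test conditions to choose from. And a reader of Section I cannot tell how large an arm difference 60 patients could show.

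**Working it through.** **1. What an arm comparison needs, against what is written**

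| Needed | Primary (prefrontal NIRS) | Secondary (still symptomatic at week 8) |
|---|---|---|
| Assigned arm in the analysis | Absent from Section H | No analysis given |
| Visit or time point of the contrast | Not named | Week 8, from the endpoint definition |
| Baseline handling | Not stated | Not stated |
| Scale and cut-off | Level or change not stated | Not stated |
| Detectable arm difference | Absent from Section I | Absent from Section I |

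The public version omits some text, but Sections H and I, where these items belong, are present.

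**2. The plan's own figure**

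Inputs from Section I: N = 60, alpha 0.05, power 0.80, R-squared 0.31. In a multiple-regression F test with noncentrality N × R²/(1 − R²), the smallest detectable R-squared at N = 60 is 0.12, 0.145, 0.16 and 0.18 for 1, 2, 3 and 4 predictors. The stated 0.31 is therefore not reproduced; it is conservative for that test, with power about 99% or more at 1 to 4 predictors. Its derivation should be stated. It describes the flow-CO2 relation and gives no power for arm.

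**3. Detectable arm difference, continuous outcome**

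Inputs: 60/2 = 30 per arm (Section D(1)); alpha 0.05 taken as two-sided, since Section I does not say; power 0.80. Assumed: 20% loss, giving 30 × 0.8 = 24 per arm, and correlation r between the visit-1 and week-8 values.

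- Normal approximation: (1.960 + 0.842) × √(2/30) = 0.72 SD. The exact noncentral t gives 0.736 SD.
- With 24 per arm, the noncentral t gives 0.826 SD.
- Adjustment for the visit-1 value multiplies by √(1 − r²). At r = 0.5 and 30 per arm: 0.736 × 0.866 = 0.64 SD.

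| Per arm | Unadjusted | r = 0.3 | r = 0.5 | r = 0.7 |
|---|---|---|---|---|
| 30 | 0.74 SD | 0.70 | 0.64 | 0.53 |
| 24 | 0.83 SD | 0.79 | 0.72 | 0.59 |

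Unadjusted power with 30 per arm is 21% at 0.3 SD, 48% at 0.5 SD and 86% at 0.8 SD.

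**4. Week-8 proportion still symptomatic**

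The documents give no usual-care rate, so 30%, 40% and 50% are assumed. Exact enumeration finds the exercise-arm rate at which the Newcombe 95% interval for the difference excludes zero with probability 0.80.

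| Assumed usual-care rate | Detectable, 30 per arm | Detectable, 24 per arm |
|---|---|---|
| 30% | 3.9% (fall of 26 points) | 2.3% (28 points) |
| 40% | 9.8% (30 points) | 7.7% (32 points) |
| 50% | 16.7% (33 points) | 13.9% (36 points) |

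With equal observed proportions near these rates, the interval is about ±22 to 24 points with 30 per arm and ±25 to 26 with 24. This endpoint is coarse and is best reported as an interval.

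**The case against.** **The exercise protocol may be the graded test.** The Figure 1 caption, "Modified sub-maximal exercise protocol", belongs to the cycle test, and Section D(3) records flow before, during and after it. On that reading the primary is a within-session change, and the missing arm term does not contradict the primary as worded. This stands as a point about wording. It does not close the gap: the programme's effect on that change, and on persistent symptoms, still has no analysis.

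**The study calls itself physiology.** Section G describes physiologic investigation, not clinical trials. That sentence explains the lack of a formal quality assurance programme. It does not cancel the randomisation, Aim 2 or the week-8 symptom endpoint.

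**Section H names the effect of exercise as a goal, and a mixed model suggests repeated measures.** Both are true, but no contrast, visit effect or random-effect structure follows.

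**Inferences a reader might draw that the documents do not support:**

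- *That the design is sound and only the write-up is lacking.* The text available gives no allocation method, concealment, or timing of allocation relative to visit 1. Section D(5) also conflicts with itself: usual care receives no heart-rate-specific recommendation, yet at visit 2 the target heart rate is adjusted for every participant still symptomatic. If applied to both arms, that could blur the contrast.
- *That the blinding step proves an arm comparison was intended.* Section F keeps exercise logs apart "to help blind the PI from knowing which intervention group the subjects are in", but Section D(1) calls the study non-blinded. The case rests on the randomisation and Aim 2.
- *That the sample is too small.* The documents state no target arm difference, so this cannot be judged.
- *That an elaborate arm-by-slope model is required.* A baseline-adjusted arm contrast closes the gap.

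**Conclusion.** The concern holds and must be fixed. The only specified model contains no arm, visit or arm-by-visit term; neither endpoint has a planned arm comparison; and the sample size speaks only to the flow-CO2 relation. This conclusion comes from reading Sections H and I and needs no assumed number. It holds under either meaning of the exercise protocol, although that meaning decides whether the primary outcome is a level or a within-session change.

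The sizes in the working rest on two-sided 0.05, 80% power and equal arms. The loss rate, baseline correlations and symptom rates are assumptions. No judgement that the randomisation itself is sound is offered or implied.

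**What to change.** **Section H**

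1. Add one prespecified week-8 comparison by randomised arm of the prefrontal NIRS outcome in Section D(4), adjusted for the visit-1 value, with all randomised patients in their assigned arm. A mixed model over visits with arm-by-visit terms and arms set equal at visit 1 is one suitable form. State whether the outcome is a level in one named test condition or the after-minus-before change in the graded test. The latter needs NIRS in that test for everyone, whereas Section D(5) allows Doppler or NIRS.
2. Add the week-8 proportion still symptomatic by randomised arm, as a risk difference with 95% confidence interval, naming the symptom scale and cut-off.
3. Keep the flow-CO2 model as a separate physiological analysis. Define amount of exercise and symptom duration. Label amount of exercise, and any symptom duration counted after enrolment, as exploratory and not as adjustments for the arm effect.

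**Section I**

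State that R-squared 0.31 concerns the flow-CO2 relation and how it was derived. Add the detectable arm difference: about 0.74 SD unadjusted with 30 per arm, 0.83 SD with 24 per arm (20% loss assumed), and 0.64 SD with 30 per arm after adjustment at an assumed correlation of 0.5.

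**Section D(5)**

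Reconcile the two statements on which participants receive a target heart rate.

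**Cost.** Wording, chiefly in Sections H and I, and a little more analysis. No new patients or visits. If the within-session change is chosen, NIRS during the graded test must be assured.
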